## Appendix 1. Mayo Score (Modified)

### < Partial Mayo Score >

Subject ID \_\_\_\_\_ Initials \_\_\_\_\_ Visit No \_\_\_\_\_ Date \_\_\_\_\_

#### Partial Mayo Scoring Index Assessment for Ulcerative Colitis Activity

Patient, please enter number of daily bowel movements you would have when in remission or before your diagnosis or symptoms of ulcerative colitis began. **This number will be Your Normal.**

#### Patient, please complete Questions 1 and 2.

Q1. Stool Frequency\* (based on the past 3 days)

- Normal number of stools = 0  
 1-2 stools more than normal = 1  
 3-4 stools more than normal = 2  
 5 or more stools more than normal = 3

Q2. Rectal Bleeding\* (based on the past 3 days)

- No blood seen = 0  
 Streaks of blood with stool less than half the time = 1  
 Obvious blood with stool most of time = 2  
 Blood alone passed = 3

\* Patient will choose the highest stool frequency and the most severe bleeding of the past 3 days.

#### Investigator, please complete Question 3.

Q3. Physician's Global Assessment\*\*

[figure not shown]
- Normal = 0  
 Mild disease = 1  
 Moderate disease = 2  
 Severe disease = 3

\*\* Physician's Global Assessment acknowledges the sub scores, the daily records of abdominal discomfort and functional assessment, and other observations such as physical findings and patient's performance status.

< Comments >

**Partial Mayo Score (Sum of all above items)**

< **Mayo Endoscopic Score** >

Site Number:		Principal Investigator:	
---------------------	--	--------------------------------	--

Subject No and Initials: \_\_\_\_\_ / \_\_\_\_\_

**Endoscopy**

Type (Cycle one):      Screening      Visit 4 (Week 8)

Date: \_\_\_\_\_

Name of GI Doctor: \_\_\_\_\_

**Mayo Endoscopic Score**

Score: \_\_\_\_\_

- 0 = Normal or inactive disease
- 1 = Mild disease (erythema, decreased vascular pattern)
- 2 = Moderate disease (marked erythema, absent vascular pattern, friability, erosions)
- 3 = Severe disease (spontaneous bleeding, ulceration)

\_\_\_\_\_  
**Investigator Signature\***

\_\_\_\_\_  
**Date (dd/mmm/yyyy)**

## Appendix 2. Ulcerative Colitis Endoscopic Index of Severity

Patient ID \_\_\_\_\_ Initials \_\_\_\_\_ Visit No \_\_\_\_\_ Date \_\_\_\_\_

**Vascular Pattern** Score: \_\_\_\_\_

- 0 = Normal (Normal vascular pattern with arborisation of capillaries clearly defined, or with blurring or patchy loss of capillary margins)
- 1 = Patchy obliteration (Patchy obliteration of vascular pattern)
- 2 = Obliterated (Complete obliteration of vascular pattern)

**Bleeding** Score: \_\_\_\_\_

- 0 = None (No visible blood)
- 1 = Mucosal (Some spots or streaks of coagulated blood on the surface of the mucosa ahead of the scope that can be washed away)
- 2 = Luminal mild (Some free liquid blood in the lumen)
- 3 = Luminal moderate or severe (Frank blood in the lumen ahead of endoscope or visible oozing from mucosa after washing intraluminal blood, or visible oozing from a hemorrhagic mucosa)

**Erosions and Ulcers** Score: \_\_\_\_\_

- 0 = None (Normal mucosa, no visible erosions or ulcers)
- 1 = Erosions (Tiny [ $\leq 5$ mm] defects in the mucosa, of a white or yellow color with a flat edge)
- 2 = Superficial ulcer (Larger [ $> 5$ mm] defects in the mucosa, which are discrete fibrin-covered ulcers when compared with erosions, but remain superficial)
- 3 = Deep ulcer (Deeper excavated defects in the mucosa, with a slightly raised edge)

Investigator \_\_\_\_\_ Date \_\_\_\_\_

### Appendix 3. Short Inflammatory Bowel Disease Questionnaire

Patient ID \_\_\_\_\_ Initials \_\_\_\_\_ Visit No \_\_\_\_\_ Date \_\_\_\_\_

This questionnaire is designed to find out how you have been feeling during the last 2 weeks. You will be asked about symptoms you have been having as a result of your inflammatory bowel disease, the way you have been feeling in general, and how your mood has been. Please check the box of your choice below each question.

1. How often has the feeling of fatigue or being tired and worn out been a problem for you during the past 2 weeks?  
All of the time  
Most of the time  
A good bit of the time  
Some of the time  
A little of the time  
Hardly any of the time  
None of the time
2. How often during the last 2 weeks have you delayed or canceled a social engagement because of your bowel problem?  
All of the time  
Most of the time  
A good bit of the time  
Some of the time  
A little of the time  
Hardly any of the time  
None of the time
3. As a result of your bowel problems, how much difficulty did you experience doing leisure or sports activities during the past 2 weeks?  
A great deal of difficulty; activities made impossible  
A lot of difficulty  
A fair bit of difficulty  
Some difficulty  
A little difficulty  
Hardly any difficulty  
No difficulty; the bowel problem did not limit sports or leisure activities
4. How often during the past 2 weeks have you been troubled by pain in the abdomen?  
All of the time  
Most of the time  
A good bit of the time  
Some of the time  
A little of the time  
Hardly any of the time  
None of the time
5. How often during the past 2 weeks have you felt depressed or discouraged?  
All of the time  
Most of the time  
A good bit of the time  
Some of the time  
A little of the time  
Hardly any of the time  
None of the time
6. Overall, in the past 2 weeks, how much of a problem have you had with passing large amounts of gas?  
A major problem  
A big problem  
A significant problem  
Some problem  
A little trouble  
Hardly any trouble  
No trouble
7. Overall, in the past 2 weeks, how much of a problem have you had maintaining or getting to the weight you would like to be?  
A major problem  
A big problem  
A significant problem  
Some problem  
A little trouble

- |   |   |
|---|---|
| 
Hardly any trouble
No trouble
 
8. How often during the past 2 weeks have you felt relaxed and free of tension?
 
All of the time
Most of the time
A good bit of the time
Some of the time
A little of the time
Hardly any of the time
None of the time
 
9. How much of the time during the past 2 weeks have you been troubled by a feeling of having to go to the bathroom even though your bowels were empty?
 | 
All of the time
Most of the time
A good bit of the time
Some of the time
A little of the time
Hardly any of the time
None of the time
 
10. How often during the past 2 weeks have you felt angry as a result of your bowel problem?
 
All of the time
Most of the time
A good bit of the time
Some of the time
A little of the time
Hardly any of the time
None of the time
 |
|---|---|

Study Coordinator \_\_\_\_\_ Date \_\_\_\_\_

1 REVISION HISTORY

SAP Version 1.0 was created and approved prior to any unblinding to the study team.

SAP Version 2.0 was planned to update a statistician of KCRN Research and Section 6 List of Tables and Figures. TFL shells were created for the 1st cohort and attached.

2 STUDY OBJECTIVES AND ENDPOINTS

2.1 Study Objectives

2.1.1 Primary Objective

The primary objective is to assess the efficacy and safety of multiple oral doses of BBT-401-1S in patients with active UC.

2.1.2 Secondary Objectives

The secondary objectives are to assess the plasma and tissue concentration of multiple oral doses of BBT-401-1S in patients with active UC and to evaluate the effects of BBT-401-1S on biomarkers.

2.2 Study Endpoints

2.2.1 Primary Endpoints

- Change from baseline in Total Mayo Score at Week 8

2.2.2 Secondary Endpoints

[figure not shown]
- Change from Baseline in Partial Mayo Score at Week 8
- Change from Baseline in Histologic Assessment of Endoscopic Biopsy at Week 8
- Change from Baseline in Ulcerative Colitis Endoscopic Index of Severity (UCEIS) Score at Week 8
- Change from Baseline in Short Inflammatory Bowel Disease Questionnaire (SIBDQ) at Week 8
- Number and Severity of Treatment Emergent Adverse Events (TEAEs) up to Week 8
- Change from Baseline in Concentration of Biomarkers (C-reactive protein [CRP], fecal calprotectin, and fecal lactoferrin) at Week 8
- Plasma and Tissue Concentration of BBT-401-1S in Patients with Active UC

3 STUDY DESIGN

3.1 Summary of Study Design

This randomized, placebo-controlled, dose-escalation, multicenter, Phase 2 study consists of three cohorts with 16-week treatment period per cohort that will be conducted sequentially. The first cohort will receive 400 mg of BBT-401-1S (starting dose). Efficacy, safety, and PK data of the first cohort will be used to select the dose of the subsequent cohort. For the 1st or 2nd cohort, if the 12th patient (75%) completes Visit 4 (Week 8), unblinding of 12 patients will be performed within 2 weeks after Visit 4 (Week 8) and the unblinding information will be only provided to the Sponsor for the analysis to determine the dose of the next cohort. A dose level may be repeated or added based on the results of the previous cohort(s).

Patients will receive a daily oral dose of BBT 401-1S or placebo for the 16 weeks. While patients who are assigned to Active Group will receive BBT-401-1S for the first 12 weeks and then placebo for the last 4 weeks, patients who are assigned to Placebo Group will receive placebo for the first 8 weeks and then BBT-401-1S for last 8 weeks.

The schedule of assessments is illustrated in Table 1.

Table 1. Schedule of Assessments

	Screening	Treatment Period						SFU
		V2	V3	V4	V5	V6	ET	
Visit Number	V1							
Visit Period	Up to W-4	Baseline	W4	W8	W12	W16	N/A	W2 from LD
Visit Window	N/A	Within 28 days from V1	±3 days	±3 days	±3 days	±3 days	N/A	+ 7 days from LD
Informed Consent	X							
Demographic Information	X							
Medical/medication History	X	X						
Inclusion/exclusion Criteria	X	X						
Vital Signs	X	X	X	X	X	X	X	X
Physical Examination	X	X ^a	X	X	X	X	X	
12-lead ECG	X	X ¹	X	X	X	X	X	
Clinical Lab Tests and Serum Biomarker ²	X	X ^a	X	X	X	X	X	X
Endoscopy (biopsy)	X			X			X ³	
Randomization		X						
Mayo Score	X	X	X	X	X	X	X	
Ulcerative Colitis Endoscopic Index of Severity	X			X			X ^c	
Short Inflammatory Bowel Disease Questionnaire			X	X	X	X	X	
Fecal Biomarker ⁴			X	X	X	X	X	
Plasma Pharmacokinetics ⁵			X	X	X			
Tissue Concentration ⁶	X			X			X ^c	
Drug Dispensing (with subject diary)		X	X	X	X			
Drug Return and Compliance			X	X	X	X	X	
AE and Concomitant Medication		X	X	X	X	X ^g	X ^g	X

AE = adverse event; ECG = electrocardiogram; SFU = Safety Follow-Up; V = Visit; W = Week; ET = Early Termination; LD = Last Dose

¹ Waived if the screening visit is conducted within 10 days prior to Visit 2 (Baseline).

² Serum chemistry, hematology, coagulation test, HIV and hepatitis screens, serum hCG (women with childbearing potential only), and serum CRP (not measured at SFU).

³ Only if early termination occurs before Visit 4 (W8).

⁴ Fecal calprotectin and fecal lactoferrin. A collection container will be dispensed to patients on the previous visit.

⁵ Visit 2 (Baseline) and Visit 3 (W4): pre-dose and 3 and 6 hours post-dose; Visit 4 (W8): pre-dose only.

⁶ During the endoscopy (flexible proctosigmoidoscopy/colonoscopy) for biopsy.

^g Reviewing any changes in smoking habits of subject during the study period.

3.2 Determination of Sample Size

As this is an initial dose-escalation study, it is appropriately based on only a limited number of patients in each dose cohort. The size of the study is not based on any statistical power calculations and no formal sample size calculation has been done. Based on the experience from the previous studies and the use of a sequential dose-escalation design for this study, a total of 48 patients (16 patients per dose cohort) is considered appropriate for the study.

3.3 Treatments

Patients will receive a daily oral dose of BBT 401-1S or placebo for the 16 weeks. While patients who are assigned to Active Group will receive BBT-401-1S for the first 12 weeks and then placebo for the last 4 weeks, patients who are assigned to Placebo Group will receive placebo for the first 8 weeks and then BBT-401-1S for last 8 weeks.

3.4 Randomization and Blinding

A total of 16 subjects in each of the 3 dosing cohorts will be randomized to either active or placebo group in a 3:1 ratio (12 active and 4 placebo) using the electronic data capture (EDC) system in which the randomization code is integrated.

The randomization code will be generated by an unblinded statistician who is not involved with the study. The Sponsor, investigators, patients, and CRO and other relevant personnel involved with the conduct of the study, with the exception of clinical supply staff and the unblinded statistician, will be blinded to the identity of study medication.

For the 1st or 2nd cohort, if the 12th patient (75%) completes Visit 4 (Week 8), the CRO data management (DM) team confirm all clinical data of the 12 patients have no issue and then obtain the written consent from the Sponsor to breaking the code. Per the request of the CRO DM team, the randomization codes of the 12 patients will be opened via the unblinded statistician and notified to the Sponsor for the analysis to determine the next dose. After confirming all clinical data of remaining 4 patients for the 1st or 2nd cohort, the randomization codes will be subsequently opened to the sponsor through the same procedures stated above.

After the last patient of last cohort completes the SFU, the CRO DM team confirms the whole clinical database has no issue and then requests the database lock to the Sponsor. Per the Sponsor's approval on the database lock, the randomization code of all patients will be opened via the unblinded statistician and notified to the CRO for the statistical analysis.

Breaking of the randomization code without sponsor's permission is expressly forbidden except in the event of a medical emergency where the identity of the study medication must be known in order to properly treat the patient. In the event of a medical emergency, it is requested that the investigator make every effort to contact the study monitor or designee prior to breaking the code.

If the blind is broken due to the medical emergency, the subject must be early terminated; a written explanation must be prepared immediately.

4 STATISTICAL METHODS

4.1 General Considerations

This document describes the statistical analyses planned prior to final treatment assignment unblinding of the aggregate database. Any change to the data analysis methods described in the protocol will require an amendment ONLY if it changes a principal feature of the protocol. Any other change to the data analysis methods described in the protocol and the justification for making the change will be described in the clinical study report (CSR). Additional exploratory or ad-hoc analyses of the data will be conducted as deemed appropriate.

All tests of treatment effects will be conducted at a two-sided alpha level of 0.05 unless otherwise stated, and all confidence intervals (CI's) will be given at a two-sided 95% level, unless otherwise stated. Statistical analysis will be performed using SAS software (SAS, Version 9.1.2 or higher).

The following general terms will be used globally in the SAP:

- Unless otherwise specified, the statistical analyses will be reported using summary tables and data listings.
- Continuous variables will be summarized with n, mean, standard deviation, median, minimum, and maximum.
- Categorical variables will be summarized by counts and by percentages of subjects in corresponding categories.
- All summary tables will be presented by treatment and/or cohort.
- Individual subject data obtained from the case report form (CRFs) and any derived data will be presented by subject in data listings. Data listings will be sorted by subject, and visit date and time, if applicable.

4.2 Adjustments for Covariates

There will be no adjustment for covariates.

4.3 Analysis Sets

4.3.1 Modified Intent-to-Treat

A modified intent-to-treat (mITT) set will consist of all randomized patients who have received at least 1 dose of study medication and have at least 1 post-baseline efficacy measurement. The mITT set will be the primary set used for efficacy analyses.

4.3.2 Per-Protocol

The per-protocol set will consist of all subjects in the mITT who do not have pre-defined major protocol deviations that may affect the primary efficacy endpoint and have completed the study until Visit 4 (Week 8).

4.3.3 Safety

The safety set will consist of all subjects who have received at least 1 dose of investigational product. The safety set will be the primary analysis dataset used for safety analyses.

4.3.4 Pharmacokinetics (PK)

The PK set will consist of all subjects who have received at least 1 dose of investigational product and there is at least 1 PK sampling. The PK set will be the primary analysis dataset used for PK analyses.

4.4 Baseline and Postbaseline Definition

Unless otherwise specified, the baseline value is defined as the last value obtained before the date and time of the first dose of study drug. Post-baseline values are defined as value obtained after the first dose of study drug. Change from baseline is defined as a post-baseline value minus the baseline value.

4.5 Handling of Dropouts or Missing Data

No adjustments for missing data and no imputation methods are planned for this study.

4.6 Treatment Group Comparability

4.6.1 Patient Disposition

Subject disposition information will be summarized for all subjects. Summaries will include: the number of subjects in each analysis set, the number of subjects completed the study, and the number of subjects discontinued study and its reason. All subjects randomized in the study will be included in the summary table. Patient allocation by investigator or site will be summarized. Patient allocation by investigator or site will also be listed as well. All subjects randomized to placebo from each cohort will be pooled in Placebo group and summarized as a placebo group.

4.6.2 Protocol Deviations

Summary and listings of subjects with significant protocol deviations or violations will be provided. The following list of significant protocol violations will be determined from the clinical database and from the study clinical/medical group:

- Lack of informed consent or late informed consent
- Violations of inclusion/exclusion criteria
- Significant violations of prohibited concomitant medication usage as determined by the clinical/medical group
- Other significant protocol violations as determined by the clinical/medical group

4.6.3 Patient Characteristics

The following patient characteristics at baseline will be summarized by treatment group for all mITT patients:

- Demographic (age, gender, ethnic origin, height, weight, BMI)
- Medical history and Pre-existing condition

Medical history and pre-existing conditions will be summarized by preferred term (PT) within system organ class (SOC). Medical history is defined as illness(es) that ended prior to the signing of informed consent. Pre-existing conditions and AEs at baseline are those AEs occurring during the baseline/screening visits that are Visits 1 and 2.

4.6.4 Prior and Concomitant Therapy

Verbatim terms on eCRFs will be mapped to Anatomical Therapeutic Chemical (ATC) class and Generic Drug Names using the World Health Organization (WHO) Drug Dictionary Enhanced (WHODDE) B2 format, March 1, 2015 release.

Prior medications are defined as medications started to be taken prior to the first administration of the study drug. Concomitant medications are defined as medications started on or after the day of the first administration of the study drug during the study.

Prior and concomitant medications will be tabulated for the mITT set by WHODDE ATC level 2 classifications, preferred term, and treatment. If a subject reports the same preferred term multiple times, then the frequency of that preferred term will only be incremented by one. As with the preferred term, if a subject reports multiple medications within the same ATC level 2 classification, then the frequency of that ATC level 2 classification will only be incremented by one. Percentages will be calculated using the total number of subjects in the safety analysis set. Each summary will be ordered by descending order of incidence of preferred term within each ATC class. Prior and concomitant medications will be included in a data listing.

4.7 Efficacy Analyses

Unless otherwise specified, all efficacy analyses will be based on the mITT and subjects will be analyzed according to their randomized treatment. However, additional

sensitivity/supplementary analyses will be conducted using the PP analysis set for all efficacy endpoints.

4.7.1 Primary Efficacy Analysis

Descriptive statistics will be presented including mean, standard deviation (SD), median, max, and min by treatment and cohort group for the change from baseline to Week 8 in Total Mayo score. Also, to better assess the differences between each dose and the placebo for the change from baseline to Week 8 in Total Mayo score, a mixed model repeated measures (MMRM) analysis will be performed. The MMRM model will include treatment (whether 1st dose, 2nd dose, or 3rd dose vs. Placebo) and the baseline score as fixed effects, and center as a random effect. Restricted Maximum Likelihood (REML) with an unstructured variance-covariance matrix will be used for estimation in the MMRM analysis. If the fit of the model with the unstructured covariance structure does not converge, the following covariance structures will be tried in order until convergence is reached: Toeplitz with heterogeneity, autoregressive with heterogeneity, Toeplitz, and autoregressive. Each dose will be compared with placebo—model-based point estimates for the treatment effects and 95% confidence intervals (CIs) will be calculated.

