### 9.5.1 Analysis of Primary Endpoint

The primary objective is to determine the efficacy of BBT-401-1S in patients with active Ulcerative Colitis. Response to treatment will be evaluated using the change from baseline in Total Mayo score at week 8 based on the mITT population. The baseline value is defined as the last value obtained on or before the date and time of the first study drug dose. Descriptive statistics will be presented including mean, standard deviation (SD), median, max, and min by treatment and cohort group (and overall cohort) at each timepoint. However, to allow for a direct comparison of BBT-401-1S vs placebo for each cohort, descriptive statistics will be provided for the difference in the change from baseline between the treatment groups during the double-blind portion of the study.

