5 CHANGES TO PROTOCOL-SPECIFIED ANALYSES

No changes to protocol-specified analyses are planned.

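### The SAP's dose contrasts use one placebo group pooled over three sequential cohorts with no cohort term, and the protocol's within-cohort difference is not specified for cohorts 2 and 3 or beside the three-dose model

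*SAP*

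**What the plan says.** **Design.** SAP 3.1 says the study "consists of three cohorts with 16-week treatment period per cohort that will be conducted sequentially". SAP 3.4 randomises 16 patients in each cohort, 12 to active and 4 to placebo. On sample size, SAP 3.2 states: "The size of the study is not based on any statistical power calculations".

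**Primary model.** SAP 4.7.1 gives descriptive statistics by treatment and cohort group, then an MMRM: "The MMRM model will include treatment (whether 1st dose, 2nd dose, or 3rd dose vs. Placebo) and the baseline score as fixed effects". Center is a random effect. There is no cohort or calendar term. Each dose is compared with placebo, with a point estimate and 95% CI. SAP 4.7.2 uses similar models for the secondary efficacy endpoints.

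**Pooling.** SAP 4.6.1 says: "All subjects randomized to placebo from each cohort will be pooled in Placebo group and summarized as a placebo group". That sentence concerns the disposition summary. For efficacy, pooling follows from the single placebo level in the model.

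**Protocol.** Section 9.5.1 plans a descriptive difference in change from baseline between the treatment groups "to allow for a direct comparison of BBT-401-1S vs placebo for each cohort". Section 1.2 says the same for Week 8. Sections 9.1 and 9.5 plan no formal inferential statistics.

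**Shells and declared changes.** SAP Section 1 says the attached table shells were made for the 1st cohort. The primary shell (Table 14.2.1.1.1) has one placebo and one active column, with a p-value, LS mean difference and 95% CI. SAP Section 5 reads: "No changes to protocol-specified analyses are planned".

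**The concern.** Randomisation protects the comparison of 12 active with 4 placebo patients inside a cohort. It does not protect the comparison of one cohort's active patients with another cohort's placebo patients, which rests on the assumption that nothing but dose changed between cohorts. The model makes that assumption without stating it.

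The trial exists to inform dose, and each dose is meant to be studied in its own period. A steady shift in patients, background therapy, scoring or placebo response would therefore look like a dose-response. Zero drift is not obvious: sites are in two countries, and under SAP 4.11 the Sponsor receives unblinded results of one cohort before choosing the dose of the next. The contrast that would expose drift is the within-cohort difference promised in the protocol. Beyond the 1st-cohort shell, the SAP does not specify it.

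**Working it through.** **Inputs from the documents.** Three sequential cohorts of 16 (12 active, 4 placebo). The arithmetic agrees: 12 + 4 = 16 and 3 × 16 = 48. Two-sided alpha is 0.05 (SAP 4.1).

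**Assumptions.** The documents give no SD for the change in Total Mayo score, no effect size and no drift. I take drift as linear, d per cohort, with no true drug effect and no dropout. SDs of 2, 2.5 and 3 points are illustrative.

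**1. Non-concurrent share.** The placebo level holds 3 × 4 = 12 patients. For any dose, 4 are concurrent and 8 are not: 8/12 = two thirds.

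**2. Bias.** With drift, cohort means are 0, d and 2d. The pooled placebo mean is (0 + d + 2d)/3 = d.
- Dose 1: 0 - d = -d
- Dose 2: d - d = 0
- Dose 3: 2d - d = +d

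The false gap between dose 3 and dose 1 is 2d. For d = 0.25, 0.5 or 1 point, that is 0.5, 1 or 2 points.

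**3. Precision.** SE = SD × sqrt(1/n1 + 1/n2).
- Pooled, 12 v 12: sqrt(1/12 + 1/12) = 0.408 SD
- Within cohort, 12 v 4: sqrt(1/12 + 1/4) = 0.577 SD
- Ratio: 0.577/0.408 = 1.41, so twice the variance

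95% CI half-widths in points:

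| SD | Pooled (43 df) | Cohort term (41 df) | One cohort alone (14 df) |
|---|---|---|---|
| 2 | 1.65 | 2.33 | 2.48 |
| 2.5 | 2.06 | 2.91 | 3.10 |
| 3 | 2.47 | 3.50 | 3.71 |

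**4. Bias against variance.** In units of SD², the mean squared error (MSE) for an outer dose is 0.167 + d² pooled and 0.333 within cohort. They are equal at d² = 0.333 - 0.167, so d = 0.41 SD. Below that the pooled estimate is the better one. For dose 2 under linear drift it is always better.

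**5. False positives.** Simulated two-sample t tests with unit SD, dose 3 against pooled placebo, reject in 5% of trials at d = 0, about 5.6% at 0.1 SD, about 9% at 0.25 SD and about 19% at 0.5 SD. Dose 2 stays at or below about 5%, and the concurrent 12 v 4 test stays at 5%. A noncentral t calculation with 44 df, which ignores the extra spread that drift adds to the residual, gives 9.2% and 22.4% at 0.25 and 0.5 SD.

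**6. What the center term removes.** This was simulated with 2,000 trials per setting, SD 2.5, 8 assumed sites and center variance fixed at 0.25 or 1.0.
- Calendar drift of 1 point per cohort with stable sites: bias with random center is -1.00, 0.02 and 1.00 (center variance 0.25), so nothing is removed.
- Change in site mix only (site groups 2 points apart, share of the second group 10%, 50%, 90%): outer-dose bias falls from about 0.8 to about 0.7 (center variance 0.25) or 0.5 (1.0).
- Adding a cohort term brings all biases to about 0 in both settings.

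**7. Is a cohort term estimable?** Yes. Intercept, three doses and two cohort indicators give a design matrix of rank 6 of 6, because every cohort has its own placebo patients. Without baseline and center, each dose effect then equals the within-cohort difference.

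**The case against.** The case for leaving the plan alone has real substance.

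- **Pooling buys precision.** Four placebo patients per cohort is very few, and pooling halves the variance. Under linear drift below about 0.41 SD the pooled estimate has the lower MSE for the outer doses. This stands, and it is why the pooled estimate should stay.
- **The drift sizes are hypothetical.** At SD 2.5, d = 0.5 SD would mean a shift of 2 × 0.5 × 2.5 = 2.5 points between cohorts 1 and 3, which is large. At d = 0.1 SD the error rate barely moves. This stands, so the percentages are illustrations only.
- **No confirmatory claim depends on this.** The study has no power basis and the protocol plans no formal inference. This limits the weight. It does not remove the point, because the SAP adds tests at 0.05 and intervals, and the shells print p-values.

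Some stronger readings are tempting but the documents do not support them.

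- A reader might infer that the per-cohort comparison has been abandoned. It has not: group means by cohort remain, and the 1st-cohort shell shows the concurrent difference with 95% CI. Subtracting printed means for cohorts 2 and 3, however, gives no interval.
- A reader might infer that dose is wholly inseparable from cohort. Each cohort has randomised placebo patients, so the two can be separated. A dose level may also be repeated. The confounding lies in the chosen contrast.
- A reader might infer that site differences are uncontrolled. Random center absorbs part of a change in site mix, and the baseline score adjusts for entry severity.
- A reader might take SAP 4.6.1 as the rule for efficacy pooling. It concerns disposition. Protocol 9.5.1 itself asks for overall-cohort summaries, so combining cohorts is not foreign to it.

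**Conclusion.** The point holds in a limited form. The model's dose contrasts use a placebo group that is two thirds non-concurrent, with no cohort term and no stated no-drift assumption. Additive linear drift of d per cohort passes in full into the outer-dose contrasts (-d and +d) when it occurs within sites, and in part when it comes from a changing site mix. The within-cohort difference promised in the protocol is not specified for cohorts 2 and 3 or beside the three-dose model. SAP Section 5 is inaccurate, because the added MMRM inference and the pooled-placebo comparison both depart from the protocol.

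The bias formula and the SE ratio follow from the planned numbers, given additive linear drift, equal variances and no dropout. The false-positive rates depend on assumed drift and on a plain t test without the model's baseline and center terms. Nothing in the documents shows that drift occurred or how large it might be. The change should be made, but the point does not invalidate the pooled analysis.

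**What to change.** 1. For all three cohorts, report the within-cohort active-minus-placebo difference in change to Week 8 with a 95% CI, next to the pooled-placebo estimate. Add the matching shells for cohorts 2 and 3 and for the three-dose model.
2. Add a sensitivity model with cohort as a fixed effect, keeping baseline and center.
3. State in SAP 4.7.1 that the pooled estimate assumes no drift between cohorts.
4. List the MMRM inference and the pooled-placebo comparison in SAP Section 5 as changes from the protocol.

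The work is SAP wording and a few table rows; no new data are needed. The statistical price is width: the within-cohort SE is 0.58 SD against 0.41 SD, so intervals are about 1.4 times wider. They are about 1.5 times wider if each cohort uses only its own residual variance (2.48/1.65 at SD 2). Because the pooled estimate stays, its precision is not lost.
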